8.3.12 Permitted and forbidden concomitant medications

All concomitant medications are authorized except nasal irrigation for patients who do not choose to use Healsea® children.

Version: **2.0**; **08** Sep **2021** Page **36** of **61** Study Number: **LPH-2101**

8.3.13 Activities performed by sponsor representatives (excluding monitoring)

The sponsor will implement and write clinical quality procedures to ensure that the clinical investigation is conducted and monitored, and that data are generated, documented, recorded, evaluated and reported in compliance with the ISO 14155:2020, the CIP, any subsequent amendment(s) and any other applicable standards and in accordance with the regulation requirements. The sponsor will ensure ongoing risk management throughout the clinical investigation and will take all measures to protect rights, safety and well-being of children who participate in the study.

The sponsor is required to report noncompliance trends and safety issues to the Ethics Committee and investigators.

The sponsor shall report on the progress and status of the clinical investigation to the Ethics Committee.

The sponsor will determine the frequency and type of audit to be performed. An audit can be used:

- i) As a routine part of the sponsor's quality assurance,
- ii) To assess the effectiveness of the monitoring activity,
- iii) Whenever there are serious or repeated CIP deviations or suspicion of fraud,
- iv) To bring an investigation site into "inspection readiness" (i.e., to prepare the investigation site for a potential regulatory inspection),
- v) When requested or suggested by a regulatory authority.
 - 8.3.14 Any known/foreseeable factors that can compromise the outcome of the clinical investigation and methods for addressing these factors

There is no known/foreseeable factor that can compromise the outcome of the clinical investigation.

8.3.15 Follow-up and medical care after completion of the study

Neither follow-up nor specific medical care for patients are foreseen after the completion of the study.

8.3.16 Potential use of samples obtained from subjects

Not applicable.

8.4 Monitoring plan

A risk-based monitoring plan included in a separate document will describe in detail who will conduct the monitoring, at what frequency monitoring will be done, at what level of detail monitoring will be performed, and the distribution of monitoring reports. Results of the risk assessment will be used to develop a risk-based monitoring plan and a supporting rationale.

8.4.1 Initiation visit

The study will only start at a site after:

Version: **2.0**; **08** Sep **2021** Page **37** of **61** Study Number: **LPH-2101**

- The Ethics Committee has granted approval for the conduct of the study,
- Essential documents are in place, such as CVs of the Investigators and site staff, and the Clinical Trial Agreement signed.

In agreeing to participate, the investigator undertakes to strictly comply with the study protocol, Good Clinical Practice, the Polish regulation and to MDR. The investigator also guarantees the authenticity of the data collected in the context of the study and agrees to the legal provisions for study sponsor quality control.

8.4.2 Monitoring

Study monitoring under responsibility of Lallemand Pharma by qualified staff will be performed at various stages of the study. Monitoring will include on-site visits and centralized data review to assure that the investigation is conducted according to the CIP and comply with applicable regulations and deadlines. On-site review of electronic Case Report Form (e-CRFs) will include the review of forms for completeness, clarity, and consistency with source documents available for each subject. In case of queries, the investigator should respond within agreed timelines.

The investigator must permit study-related monitoring visits, audits review by the Ethics Committee, and allow direct access to source data and source documents provided that subject confidentiality is protected. In case of an audit appointed by Lallemand Pharma, the investigator will receive written notification in advance.

9. Statistical design and analysis

9.1 Descriptive statistics

The cohort is described: continuous variables will be summarized using the mean, standard deviation, median, minimum, maximum and quartiles, categorical variables will be summarized using frequency counts and percentages.

Two groups (called treatment groups for a sake of simplicity) will be extracted from the cohort according to the treatment chosen by the patient and a description of each group will be performed.

Details of the statistical analyses, methods and data conventions will be described in the SAP.

All statistical tests will be 2-sided and performed using a 0.05 significance level.

9.2 Study population

The study population consists in all the patients included and who do not meet a "major deviation to protocol" as defined in section 12.

The safety population consists in all the patients included in this study.

Version: **2.0**; **08 Sep 2021** Page **38** of **61**

The analysis of primary and secondary endpoints will be performed on study population, safety endpoint will be performed on safety population.

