5. DEFINITION OF THE ANALYSIS SETS

Screened subjects: all subjects who signed an informed consent.

Included subjects: all screened subjects who participated in the study.

Full Analysis Set (FAS): all included subjects who used the investigational medical device at least once.

Per-Protocol (PP) Set: Efficacy population based on the FAS without patients with major protocol deviations.

Safety and Efficacy analyses will be performed on the FAS.

The analyses of the primary and one secondary (modelling of AUC on total WURSS by multivariate ANCOVA) efficacy criteria will also be performed on the PP Set.

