6.3. Statistical/Analytical issues

6.3.1. Significance level

All statistical analyses will be performed at the 0.05 global significance level (type I error rate), using two-sided tests.

The statistical results are conclusive for the primary efficacy criterion.

All the other statistical results have to be considered within a descriptive perspective and not as inferential issues. No adjustment for Type I error is done. P-values of statistical tests will be provided for information only.

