10. EFFICACY

10.1. Analysis of the primary efficacy criterion

The primary objective will be analysed by performing a t-test (or a Wilcoxon test if the normality assumption is not acceptable) between the means AUC of WURSS-K score during first ten days of symptoms in each group.

The answers of the fourteen first items of the WURSS-K questionnaire are scored **from 0 to 3** (0: negative answer; from 1 to 3: positive answer with an increasing severity level). See the daily symptom report in appendix (§13.3).

The total WURSS-K score at each time point is the sum of the scores of the fourteen first items of the WURSS-K questionnaire:

$$\text{At each time point } t: \text{WURSS}_{\text{tot}}(t) = \sum_{j \in \{1, \dots, 14\}} \text{WURSS}_j(t)$$

AUC of WURSS-K score will be computed by the method described in §6.4.6.

Subjects will be analysed on the Full Analysis Set and the Per-Protocol Set.

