12. CHANGES IN THE CONDUCT OF THE STUDY OR PLANNED ANALYSIS

The cold symptoms' duration was defined in the protocol as the number of symptomatic days between D1 and the first day the subject reports not having the symptom for two consecutive days.

Since several patients still reported having symptoms while they reported they did not feel sick anymore at the question 1 during the two last days of completion of the WURSS-K questionnaire, their positive answers to the cold symptoms' items have been considered as non-significant. Consequently, the question 1 has been taken into account instead of the corresponding items to determine the end of the cold symptoms' duration, however only on the condition that the two last days of completion were consecutive.

If the two last days of completion were not consecutive, positive answers to cold symptoms' items are still considered as symptomatic, even if the two last answers to the question 1 are negative. The symptom ends at the last symptomatic day if the patient reported the absence of this symptom after this day. Otherwise, the duration of the symptom is censored at D30 or at the end of the study, whichever occurs first.

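### Protocol and SAP put the only conclusive test on different analysis sets, no text says which set decides, and SAP 12 does not record the change

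*Protocol*

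**What the plan says.** Protocol 9.2 defines its efficacy set as follows: "The study population consists in all the patients included and who do not meet a" major deviation, with the major deviations listed in Protocol 12. It then assigns the analyses: "The analysis of primary and secondary endpoints will be performed on study population, safety endpoint will be performed on safety population". It names no other efficacy set.

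SAP 1 says that the SAP is based on version 2 of the protocol, dated 8 September 2021, which is the version reviewed here. SAP 5 nevertheless states: "Safety and Efficacy analyses will be performed on the FAS". It defines the FAS as "all included subjects who used the investigational medical device at least once" and the PP set as the FAS without major deviators. It adds that the primary and one secondary "efficacy criteria will also be performed on the PP Set". SAP 10.1 puts the two sets side by side for the primary criterion: "Subjects will be analysed on the Full Analysis Set and the Per-Protocol Set". The table list in SAP 13.1 plans one results table for each set (14.2.1.1 and 14.2.1.2).

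On the status of the result, SAP 6.3.1 says: "The statistical results are conclusive for the primary efficacy criterion". No set is named there. All other results are treated as descriptive.

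SAP 12, which is reserved for changes to the planned analysis, has one entry. It concerns symptom duration, which "was defined in the protocol as the number of symptomatic days between D1 and the first day the subject reports not having the symptom" (confirmed over two days running). The change of analysis set is not mentioned.

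**The concern.** The study has one conclusive test, and the documents do not agree on which children it is run. The protocol points to a set without major deviators. The SAP points to a set that keeps them, then repeats the test without them, and gives no rule for reading results that disagree.

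The choice can matter. Under Protocol 12 and SAP 7.2, missing diary assessments and nasal irrigation by children who did not choose the device are major deviations. Both arise after Visit 1, and the second can remove children from one group only. In an open-label study with self-chosen treatment, the two sets may therefore differ by more than chance.

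Timing adds to the need for a record. SAP 12 argues from how several patients answered the diary, so some outcome data were known when it was written. Nothing in it shows that group results were known. A change of primary set should still be dated and explained.

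**Working it through.** **1. The plan's own figure.** Protocol 7.4 and SAP 4 give 100 children per group for a standardised difference of 0.4, 80% power and 5% type I error. Protocol 9.1 makes the tests two-sided.
- n per group = 2 × (1.960 + 0.842)² / 0.4² = 98.1, rounded up to 99.
- Power at 100 per group = Φ(0.4 × √50 − 1.960) = Φ(0.868) = 0.807. The exact noncentral t value is 0.804.

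The figure reproduces, so the point does not rest on a sample-size error.

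**2. The sets compared.**

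| Set | Definition | Conventional-therapy children, read literally |
|---|---|---|
| Protocol study population | Included, minus major deviations | Kept |
| SAP FAS | Included, device used at least once | None |
| SAP PP | FAS, minus major deviations | None |

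The PP set resembles the protocol's study population but is not the same set. The mock tables in SAP 13.2 show a conventional-therapy column for both FAS and PP outputs, so the authors evidently meant both groups to be present. The written definition does not provide for that. As worded, neither SAP set can support a two-group comparison, so naming the FAS as primary is not enough on its own.

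**3. Error rate if either set could carry the conclusion.** This step takes the intended sets, with both groups present and PP nested in FAS. With no true effect, and exclusions unrelated to outcome and equal in the two groups, the two test statistics are approximately bivariate normal with correlation ρ = √(n_PP / n_FAS). Then

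P(at least one significant) = 1 − P(|Z₁| ≤ 1.96 and |Z₂| ≤ 1.96).

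The documents give no deviation rate, so exclusions of 5% to 20% are assumed. The last column gives power on the reduced set, Φ(0.4 × √(n/2) − 1.960), with the exact t value after the slash.

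| Excluded | n per group | ρ | P(at least one significant) | Power on the reduced set |
|---|---|---|---|---|
| 5% | 95 | 0.975 | 6.04% | 78.7% / 78.3% |
| 10% | 90 | 0.949 | 6.48% | 76.5% / 76.1% |
| 15% | 85 | 0.922 | 6.81% | 74.1% / 73.7% |
| 20% | 80 | 0.894 | 7.09% | 71.6% / 71.0% |

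The excess over 5% is 1.0 to 2.1 percentage points. The figure for two independent tests, 1 − 0.95² = 9.75%, does not apply, because the sets share most of their children.

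**4. With one named set.** A single test keeps the nominal 5% level. With all 100 per group contributing an AUC, power stays at 80.4% to 80.7%. With 10% excluded it is about 76%.

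**The case against.** The strongest reply is that the SAP does imply an order. SAP 5 first places efficacy on the FAS and only then adds the PP set, using the word also. The FAS is the set for baseline, for dropouts and for every other secondary analysis, and PP appears only as a repeat of the two AUC analyses. That stands as an indication that the FAS leads. It does not settle the matter, because SAP 10.1 lists the two sets without ranking them, SAP 6.3.1 names neither, and the protocol names the other kind of set.

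A second reply is that the SAP may define the populations. SAP 1 says that it does, Protocol 9.1 leaves details to it, and Protocol 10.3 links the definition of the populations to the data review before lock. This gives the SAP room, and SAP 5 states its sets openly. But Protocol 9.2 had already fixed the efficacy set, so moving it changes the planned analysis and belongs in SAP 12.

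A third reply is that the effect on the error rate is small and conditional. That is correct. Under SAP 6.4.6, a child without a D1 score, or without any later score up to D11, has no AUC and drops out of both analyses. The sets then differ by less than a raw count of deviations suggests. The treatment groups are also self-chosen and the primary test is unadjusted, so confounding may affect a treatment claim more than this excess does.

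A reader might infer that the plan sets up two equal conclusive tests and so breaks its 5% level. The documents do not support that, since no text lets significance in either set count as success. A reader might also infer that the protocol licenses a claim on the SAP's PP result. It does not strictly do so, because that set is defined differently from the protocol's.

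**Conclusion.** The point holds as a contradiction between the documents about the one conclusive test. The protocol fixes a set without major deviators. The SAP moves to the FAS with a PP repeat, does not say which one decides, and does not record the move. The FAS is the more natural reading of the SAP, but only by implication.

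The 5% level is not secured, which is a weaker statement than saying it is lost. It would rise to about 6.0% to 7.1% only if either set could carry the conclusion. Those figures assume 5% to 20% exclusions, equal in the two groups and unrelated to outcome, and nested sets that contain both groups. The more basic difficulty is the FAS definition: read literally, it leaves no comparison group in either SAP set, so the definitions have to be repaired together with the ranking.

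**What to change.** - **SAP 5:** define the FAS as all included children, analysed by the group chosen at Visit 1. Define the PP set as that FAS minus children with major deviations.
- **SAP 5, 6.3.1 and 10.1:** name the primary test on the redefined FAS as the single conclusive test. Label the PP test supportive, with its p-value for information only, and say that the FAS result stands if the two disagree.
- **SAP 12:** add an entry recording the move from the Protocol 9.2 study population to the FAS, with the reason.
- **Protocol 9.2:** align the text with the SAP, by amendment as Protocol 11 requires.

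The redefined FAS would also coincide with the protocol's safety population of all included patients, which SAP 5 and 11 currently replace with the device-use FAS.

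The cost is a few sentences in the SAP and one protocol amendment. No new data, patients or tables are needed, because results tables for both sets are already planned.

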9.3 Primary endpoint

The primary objective will be analysed by performing a t-test (or a Wilcoxon test if the normality assumption is not acceptable) between the means AUC of WURSS-K score during first 10 days of symptoms in each group.

9.4 Secondary endpoints

The analysis of the secondary endpoints will involve multivariate analysis.

The selection of variables in multivariate analysis will be performed using a 0.2 significance level and a stepwise method. Whole the multivariate analyses specified below involve the treatment and, in order to adjust for confounding, all the potential confounding factors as explanatory variables.

The analysis of the impact of the treatment chosen on the primary endpoint will be enriched by means of a multivariate regression model with the AUC of the WURSS-K during first 10 days of symptoms as dependent variable.

The impact of the treatment chosen on the cold symptoms' duration will be analysed by means of a Cox model.

The impact of the treatment chosen on the risk to develop respiratory complication requiring antibiotic prescription during a 20-day follow-up period will be analyzed by a multivariate logistic model.

The impact of the treatment chosen on the intake of conventional common cold medication (antibiotics, antipyretics, mucolytics, decongestants, antitussives, systemic and topical corticosteroids) will be analyzed by multivariate Poisson regressions for the numbers of days and a multivariate logistic regression for the frequency.

The impact of the treatment chosen on the number of family members in close contact developing common cold symptoms after the patient all over the study period will be analyzed by means of a multivariate Poisson regression.

9.5 Safety

All adverse events/incidents/expected side effects will be listed, but only treatment-emergent adverse events/incidents (non-serious + serious) will be summarized.

Two groups (called treatment groups) will be extracted from the cohort according to the treatment chosen by the patient.

Page **39** of **61** Version: 2.0; 08 Sep 2021

Adverse events/incidents/expected side effects will be summarized by the number and percentage of patients (by treatment group), classified by System Organ Class and Preferred Term as defined by MedDRA dictionary.

For a given treatment group, a given adverse event will be counted treatment emergent only once per patient during the treatment period.

Frequency and percentage of patients with at least one reported adverse event/incident / expected side effects will be tabulated by System Organ Class and by treatment group.

10. Data management

Subject data will be entered into an electronic case report form.

10.1 Source documents

The source documents (e.g., medical file, clinical and office charts, laboratory reports...) which contain the source of data recorded in the CRF should be specified. The e-diary will be used as source document for WURSS-K, compliance, contamination of relatives if applicable.

Each subject will be assigned and identified by a unique Screening Number. Any reference made to an individual subject within the study must be done using the unique Screening Number.

10.2 Methods for data entry and collection

A validated electronic case report form (eCRF, e-Diary, VIEDOC software) will be used to collect clinical data for this study. Some of the study data will be recorded in the e-diary (ViedocMe) by the legal guardian after secure logging to the study website (https://me.viedoc.net) and will be automatically uploaded in the e-CRF:

- WURSS-K,
- Healsea® Children use if applicable,
- Adverse event/ incidents/ expected side effects and concomitant treatments,
- Contamination of relative(s) if applicable.

Lallemand Pharma is responsible for designing the e-CRF. eCRF training will be given to appropriate personnel before/at initiation of the investigation site(s). Legal guardians will be instructed how to connect to the e-diary at visit 1.

10.3 Data review

The Data Management process includes all activities related to data handling regarding:

Version: **2.0**; **08** Sep **2021** Page **40** of **61**

- Set-up of eCRF and database
- Specification of on-line checks
- Data entry/Data editing
- Export of data from e-CRF to SAS
- Creation of post-entry checks and listings
- Clean-file process including execution of post-entry checks and listings
- Post clean-file tasks

Data entry will be done by investigators and other authorized personnel at the site(s). When entering data, on-line checks are encoded in the e-CRF for consistency and validation. Whenever required, queries issued from this review will be submitted to the investigator for resolution and then tracked until corrections are entered and validated.

A clean-file review meeting will be held prior to database lock.

The review process prepared by the clinical research assistant, data manager, study monitor, medical manager and statistician will be completed by a meeting (Validation Committee) to be attended by at least the following:

- Coordinating investigator,
- Study monitor,
- Sponsor Vigilance representative,
- Study Coordinator,
- Data manager,
- Statistician.

The review is also required for defining the analysis populations and validating the statistical analysis plan.

The meeting will be documented by written and signed minutes that will act as the basis for data processing by the Biometrics Department.

All decisions on the evaluability of the data from each individual subject for the statistical analysis must be made and documented before locking the database.

Data will be retained for at least 15 years after investigation closure. All data collected in the electronic Case Report Forms will be handled and archived under the responsibility of Lallemand Pharma.

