7.3 Secondary Objectives

- To assess the impact of both treatment modalities to reduce the duration of each infectious rhinitis symptom as rated by the Wisconsin Upper Respiratory Symptom Survey for kids (WURSS-K) [18].
- To assess the impact of both treatment modalities to reduce complications of the acute phase during a 20-day follow-up phase.
- To assess the impact of both treatment modalities on the intake of conventional common cold medication (antibiotics, antipyretics, mucolytics, decongestants, antitussives, systemic and topical corticosteroids).

Version: **2.0**; **08** Sep **2021** Page **28** of **61**

- To assess the impact of both treatment modalities to reduce the person-to-person cold spreading among close contacts (parents, siblings).
- Safety: to assess systemic and local tolerance of Healsea® Children over the study period.

7.4 Scientific justification and clinical relevance for effect sizes, noninferiority margins or equivalence

This is a prospective, open label, observational study. An arbitrary cohort of 200 children has been chosen. A cohort of 100-exposed and 100-not exposed patients is anticipated to allow to demonstrate the interest of using Healsea® Children in the allergic paediatric population. Indeed, 100 patients by arms are enough to detect a Cohen's effect size of 0.4 with a power of 80% and a type I error of 5%. Cohen's effect size is defined as the standardized difference between AUC in groups. Following Cohen's methodology, 0.4 is an intermediate size between a small effect (0.2) and a medium effect (0.5) and is coherent with the expected result.

The recruitment will be competitive in both group, exposed to Healsea Children or not exposed to Healsea® Children. However, when 100 patients will be recruited in one group, the recruitment will be stopped in this group but will continue in the other group until 100 patients to be enrolled.

No assumption of expected outcomes across treatment group is performed.

Risks and anticipated adverse effects that are to be assessed

No specific risk for subject in participating in the study is identified, provided that the eligibility criteria are fulfilled. Nevertheless, the safety and well-being of subjects will be monitored throughout the study.

8. Design of the clinical investigation

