8.1 General

8.1.1 Design type of clinical investigation

This is a prospective, open label, observational, national (Poland), multicentre study.

During this prospective observational study, one cohort of IgE-dependent allergic children with early symptoms of infectious rhinitis will be followed, children being treated with Healsea® Children on top of common cold conventional therapies or with conventional therapies only (nasal irrigation excepted). This observational study aimed to confirm the benefit of Healsea® Children in a real life setting in children with perennial allergy.

Page 29 of 61 Version: 2.0; 08 Sep 2021

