7.2. Protocol deviations

Protocol deviations will be discussed during the data review meeting and the status (minor or major) of these deviations will be validated in order to identify the subjects to be excluded from the Per-Protocol Set.

Major deviations are defined by:

- Non-compliance with the inclusion or exclusion criteria;
- No assessment of the primary efficacy criterion (WURSS-K) at D1, D5±1 and D10±1 during the treatment period;
- Intake of forbidden medication, i.e. nasal irrigation for patient who chose to not take Healsea® Children.

All other deviations will a priori be considered as minor, e.g.:

- Visits' dates not conform to the flow chart of the study;
- Compliance of the product Healsea® Children (see §9) not between 80% and 120%.

Major and minor deviations will be described by treatment group and overall. A listing of all deviations will be provided for all included subjects, including the type (major/minor).

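### An unmasked pre-lock review of open-label data defines the analysis populations and validates the SAP, while the primary test and the main efficacy population are not pinned down

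*Protocol*

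**What the plan says.** - **The review.** Protocol 10.3 schedules a clean-file meeting before database lock. Those attending include the coordinating investigator, the sponsor's vigilance representative, the data manager and the statistician. Its remit: "The review is also required for defining the analysis populations and validating the statistical analysis plan". Decisions on evaluability must be documented before lock.
- **Deviations.** SAP 7.2: "Protocol deviations will be discussed during the data review meeting and the status (minor or major) of these deviations will be validated". The result fixes the Per-Protocol (PP) Set. Both documents list the same three major deviations; everything else is minor by presumption only.
- **Masking.** Protocol 8.1.1: "This is a prospective, open label, observational, national (Poland), multicentre study". Protocol 8.1.2, on measures against bias, is marked not applicable. Under protocol 10.2 the WURSS-K and device use upload automatically from the e-diary to the e-CRF.
- **Primary test.** Protocol 9.3 and SAP 10.1 give a t-test, "or a Wilcoxon test if the normality assumption is not acceptable".
- **Main population.** Protocol 9.2 analyses efficacy in included patients without a major deviation. SAP 5 analyses efficacy on the FAS and repeats the primary analysis on the PP Set.
- **Changes.** SAP 12 reports one change, to the symptom-duration rule, and explains it from the data: "Since several patients still reported having symptoms while they reported they did not feel sick anymore at the question 1".
- **Status of results.** SAP 6.3.1 treats only the primary criterion as conclusive; other p-values are for information.

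**The concern.** In a blinded trial, settling populations and the SAP before lock keeps those decisions apart from the comparison between groups. Here it does not do so by itself. Each child's group is known, and the scores are in the e-CRF well before lock. Nothing in either document keeps group or WURSS-K out of the material the committee works from.

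That matters because two ingredients of the primary result are still open or inconsistent. No criterion, decision-maker or decision time is given for moving from the t-test to the Wilcoxon test. The population behind the conclusive test depends on which document is followed. If either were resolved after the scores had been looked at by group, a nominal 0.05 would no longer be the actual error rate, and the plan could not show otherwise.

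**Working it through.** **Inputs from the documents.** Protocol 9.1: "All statistical tests will be 2-sided and performed using a 0.05 significance level". Protocol 7.4: "A cohort of 100-exposed and 100-not exposed patients is anticipated", for a standardised AUC difference of 0.4 with 80% power. The documents give neither the shape of the AUC distribution nor an expected number of major deviators; both are assumed below.

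**The plan's own figure.** Per arm, n = 2(z₀.₉₇₅ + z₀.₈₀)²/d² = 2(1.960 + 0.842)²/0.4² = 2 × 7.85/0.16 = 98.1, so 99. The exact t calculation gives 99.08, so 100, with power 0.804. The stated 100 per arm reproduces. Sample size is not the issue.

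**Effect of leaving the test open.** Simulation with no true difference, 100 per arm, two-sided 0.05, 40,000 runs per setting. Monte Carlo SE is √(0.06 × 0.94/40,000) = 0.0012. Ranges cover three repeat runs. The last column uses 8,000 runs and takes the Wilcoxon test if Shapiro-Wilk has p < 0.05 in either group.

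| Assumed AUC shape | t-test only | Wilcoxon only | Smaller p kept | Normality rule fixed in advance |
|---|---|---|---|---|
| Normal | 5.0–5.2% | 4.9–5.0% | 6.0% | 5.2% |
| Gamma, shape 2 | 4.9–5.0% | 4.9–5.2% | 6.6–6.9% | 4.7% |
| Lognormal, σ 0.8 | 4.7–4.8% | 4.9–5.0% | 7.4% | 4.9% |

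A separate set of 4,000 runs gave 6.75% (gamma 2), 7.8% (gamma 1) and 7.7% (lognormal 0.8) for the smaller p, with SE about √(0.078 × 0.922/4,000) = 0.004. Over both sets, the skewed cases span 6.6–7.8%.

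**Effect of leaving the population open.** These are also worst cases.

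- Keeping the better t-test from all patients or from a set with random exclusions gives 5.6–6.0% with 5 excluded per arm, 6.1–6.5% with 10 and 6.7–7.2% with 20.
- Leaving both test and population open gives 7.1–10.3%.
- Knowingly removing the 1, 2, 3 or 5 highest-AUC device patients (normal data) gives 5.5%, 7.0%, 8.6% or 13.0%. This matters for the conclusive result only if the population without major deviators carries it.

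**The texts side by side.** Under protocol 9.2, major/minor status decides who enters the primary analysis. Under SAP 5 it decides only who enters the additional PP analysis. SAP 12 does not list this as a change. On the test, protocol 9.3 and SAP 10.1 agree with each other, but the protocol synopsis names only a multivariable regression for the same endpoint.

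**The case against.** The case for the plan has real content, and most of it limits the point.

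- **Test choice.** A reader might infer that the meeting picks the primary test. No text says so. The conditional rule is already in protocol version 2.0 and turns on normality, not on the result. Choosing by normality is not keeping the smaller p-value, and with a written criterion the error stays at 4.7–5.2%. What remains is that no criterion or decision time is written.
- **Populations.** The major deviations were listed in advance, and under SAP 5 their classification cannot alter the FAS result. That stands for the SAP. It does not stand under protocol 9.2, and a presumption that other deviations are minor leaves room to reclassify.
- **SAP 12.** A reader might infer that the primary analysis was tuned to the data. The documents do not support this. The change concerns symptom duration, a descriptive secondary endpoint; it does not enter the AUC calculation in SAP 6.4.6; it is openly disclosed with a data-consistency reason; and it mentions neither treatment group nor the meeting. It shows only that diary answers were seen before the SAP text was final.
- **Process controls.** Signed minutes, an audit trail of data changes and no interim analysis are genuine safeguards. Having access to individual records is also not the same as seeing a comparison by group. But these controls document decisions; they do not mask them.
- **Timing.** The text available for this review carries no SAP date or sign-off, so timing against database lock cannot be checked either way.

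**Conclusion.** The point holds as a weakness of process. An unmasked review of open-label data is given the job of defining populations and validating the SAP, the SAP was not final when diary answers were seen, and the primary test and main population are not uniquely fixed across the documents.

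The 6.6–7.8% is an upper-bound scenario. It assumes skewed AUCs, exchangeable groups with no true difference, and someone running both tests and keeping the better. It is neither an estimate of this trial's error rate nor evidence that selection took place; if the AUC is close to normal, the same conduct gives about 6.0%. With test and population fixed beforehand, the error is about 5% and 100 per arm is unchanged. The weakness is therefore modest in size, avoidable, and relevant because SAP 6.3.1 rests its only conclusive claim on this test.

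**What to change.** 1. Finalise, date and sign the SAP before outcome data are extracted or reviewed. Limit the meeting to applying it.
2. Name one primary population, reconcile protocol 9.2 with SAP 5, and record the change in SAP 12. If the FAS is kept, reword its definition: by requiring device use at least once, it literally admits no comparison patients.
3. Fix one primary test regardless of normality, for example the Welch t-test or the adjusted model, with the Wilcoxon test as a sensitivity analysis. If the adjusted model is chosen, fix its covariates in advance instead of selecting them stepwise.
4. Apply by program the major-deviation rules that can be programmed. For the WURSS-K rule, first state whether missing any one of the three time points counts, or only missing all of them. Eligibility cannot be fully programmed, because some non-inclusion criteria (protocol 8.3.1.2) rest on the investigator's judgement.
5. Have the remaining deviations classified from listings without treatment group, device use or WURSS-K values. The device-compliance deviation (minor by default) exists only for device users and would reveal the group, so handle it by program outside those listings.

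Cost: slightly more programming before the meeting, with no additional patients or staff.
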